9.4. Randomization and Blinding

This study will be conducted in a double-blind, placebo-controlled manner. Allocation to one of two treatment groups (OCA or placebo) will occur on a 1:1 ratio across sites and will be stratified by UDCA treatment (yes/no) and mean baseline bilirubin categories ($>ULN/\leq ULN$), as specified by the central laboratory. The randomization will be based on a predefined randomization code (generated by the Sponsor or designee) using an interactive web response system (IWRS), which the Sponsor intends will serve as a computer-based subject registration system at Screening and Day 0. The IWRS will also serve as an investigational product inventory and management system and may be integrated with the study database.

The Investigator or designee will be required to register the subject in the IWRS and may be prompted to provide subject data necessary to properly randomize and allocate the subject to treatment. A randomization number will be assigned (refer to [Section 9.5.2](#) below) and investigational product dispensing information (ie, bottle number[s]) will be provided.

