13.1.2. Determination of Sample Size

The target population is subjects who are at higher risk of liver-related clinical complications. Eligible subjects will have a diagnosis of PBC with bilirubin levels $>ULN$ and $\leq 5x ULN$ and/or $ALP > 3 \times ULN$. The following assumptions were used in sample size calculations:

- Exponential survival curves, placebo survival estimate of 0.6 at 8 years with a hazard ratio of 0.60, and total study duration of 10 years (from first subject enrolled), allowing for 4 years of subject accrual and 6 years of follow up.
- Subjects will be randomized in a 1:1 ratio to placebo or OCA.
- The 2 groups will be compared using a 2-sided log rank test at the 5% level of significance.
- Two interim analyses and one final analysis are planned. The first interim analysis will be performed when 50% of the target events are accrued and the second interim will be performed when 75% of the target events are accrued.
- A dropout rate of 10% is assumed

Based on the randomization ratio, significance level, and assumed hazard ratio, a total of 127 events (both groups combined) will provide 80% power to demonstrate a statistically significant difference between OCA and placebo on time to liver-related outcomes, including all-cause mortality.

In addition, based on the remaining assumptions stated above, it is estimated that approximately 428 subjects will be enrolled to attain 127 events.

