Analyses of changes in MELD score, Child-Pugh score, MRS, IgM, CRP, TNF- α , FGF-19, CK-18, C4, and ELF score will be summarized and analyzed using the Wilcoxon Rank Sum Test to compare treatment groups. The median differences and 95% CI of the median differences between treatment groups will be constructed using Hodges-Lehmann estimate. If the median differences between treatments are not symmetrical around the median, the Sign Test may be used.

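### Section 13.1.5 allows the Sign Test, a one-sample or paired test, as an optional fallback for comparing two unpaired arms on ten exploratory scores and biomarkers

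*Protocol*

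**What the plan says.** The last paragraph of protocol Section 13.1.5, before the subsection on biochemistry and outcomes, covers "Analyses of changes in MELD score, Child-Pugh score, MRS, IgM, CRP, TNF- α , FGF-19, CK-18, C4, and ELF score". These ten variables are to be "analyzed using the Wilcoxon Rank Sum Test to compare treatment groups", and the confidence interval for the "median differences between treatment groups will be constructed using Hodges-Lehmann estimate". The paragraph closes with the fallback: "If the median differences between treatments are not symmetrical around the median, the Sign Test may be used".

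On design, Section 9.4 states: "Allocation to one of two treatment groups (OCA or placebo) will occur on a 1:1 ratio across sites". Randomisation is stratified by UDCA use and bilirubin category, but no section matches or pairs individual OCA and placebo subjects. The propensity matching in Sections 13.1.1.1 and 13.1.8 selects historical controls for time-to-event outcomes and has no bearing on these ten variables.

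Section 13.1.10 places endpoints outside the five-step hierarchy on a descriptive and exploratory footing. All ten variables fall there.

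**The concern.** The Sign Test counts how many of a set of independent differences are positive and refers that count to a binomial distribution with probability one half. The differences must come from one sample or from natural pairs. Two independent arms supply neither, so an analyst told to use the test must first invent a set of differences, and the answer then depends on the invention.

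The condition for switching also looks borrowed from paired data. There, symmetry of the differences supports the signed-rank test, and the Sign Test is the usual retreat when symmetry fails. The rank-sum test named here carries no such condition.

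At stake is whether the p-values for these variables can be interpreted. Several of them serve the secondary objective on markers of inflammation and fibrosis in Section 6.2. The protocol names both the test and its trigger, so this is a stated method and not a detail deferred to the SAP. A SAP that followed it would inherit the error.

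**Working it through.** The protocol gives no figure on this point, so there is none to reproduce. The check is part reasoning and part illustration.

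**Inputs.**
- Ten variables, counted in Section 13.1.5.
- Two independent arms, 1:1 (Section 9.4).
- 428 subjects (Section 13.1.2: "approximately 428 subjects will be enrolled to attain 127 events"), so 428 / 2 = 214 per arm, assuming all are evaluable.
- Two-sided 0.05, the level of the trial's main test ("The 2 groups will be compared using a 2-sided log rank test at the 5% level of significance").
- Assumed for illustration only: lognormal (skewed) changes, 4,000 simulated trials per scenario. The simulation error of a rejection rate near 0.05 is √(0.05 × 0.95 / 4000) ≈ 0.003.

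**Step 1: does the rank-sum test need symmetry?** Its null hypothesis is that both arms share one distribution, and its reference distribution follows from exchangeability whatever the shape. In simulation with the same skewed distribution in both arms, it rejected in 0.0535 of trials with no median change and in 0.046 with a common median change of 0.3. Both are within about one simulation error of 0.05.

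**Step 2: what does asymmetry of the differences tell us?** If OCA values are distributed as placebo values plus a constant Δ, then an OCA value minus an independent placebo value is symmetric about Δ, even when each arm is skewed. Asymmetric between-arm differences therefore show that the arms differ by more than a shift. That affects how the Hodges-Lehmann estimate is read. It does not affect the rank-sum test of equal distributions.

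**Step 3: what happens if the Sign Test is forced onto between-arm differences?** There are two ways to build the differences.

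(a) *All 214 × 214 differences, treated as independent.* Under no arm difference, the count of positive differences is the Mann-Whitney statistic.
- Its true variance is n²(2n + 1)/12, while the Sign Test assumes n²/4.
- The ratio is (2n + 1)/3 = 429/3 = 143.
- The nominal cut-off of 1.96 is then really 1.96/√143 = 0.164 standard deviations, so the false-positive rate is 2 × [1 − Φ(0.164)] ≈ 0.87.
- Simulation gave 0.875 and 0.876. This use is invalid.

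(b) *Arbitrary one-to-one pairs.* Size held, at 0.0495 and 0.047. But the p-value changes with the pairing chosen, and power at a shift of 0.25 was 0.695, against 0.8685 for the rank-sum test on the same data.

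Neither construction is better than the test the protocol already names.

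**The case against.** The strongest reply is that the trigger makes sense in its own terms. By Step 2, asymmetric between-arm differences signal that the shift model behind the Hodges-Lehmann estimate has failed, and it is reasonable to want a response. That stands as a reason to supplement the estimate. It does not make the Sign Test the right response or give grounds for dropping the rank-sum test.

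The simulations are also open to challenge. Identical distributions in both arms make the differences symmetric in the population, so the fallback should not fire in exactly that setting. Nor does the protocol say that all pairwise differences would be used. Both points are fair: the 0.87 shows that one possible implementation fails and does not measure expected harm in this trial.

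Four stronger readings are tempting, and the protocol supports none of them.
- A reader might infer that a change common to both arms could be reported as a treatment effect. That needs a within-arm or pooled Sign Test, which in the common-change simulation rejected in 0.98 to 1.00 of trials. The sentence concerns differences between treatments, so it does not describe that analysis.
- A reader might infer that every p-value from the fallback would be invalid. Arbitrary pairing keeps nominal size; its faults are arbitrariness and lost power.
- A reader might quote the normal-theory efficiency of sign to Wilcoxon procedures, (2/π)/(3/π) = 0.667. The fallback is meant for asymmetry, which that figure does not describe.
- A reader might infer that the trial's main conclusions are exposed. The wording only permits the test, and Section 13.1.10 keeps these variables outside the hierarchy.

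**Conclusion.** The sentence is wrong as written, and the matter is minor. It names an inapplicable test as an optional fallback for between-arm comparisons of ten exploratory variables. Used, it could yield an invalid p-value, or an arbitrary and less powerful one, depending on how the differences were built. Asymmetry does not justify leaving the rank-sum test; it only limits how the Hodges-Lehmann estimate may be read.

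The conclusion rests on the arms being independent and unpaired, which Section 9.4 supports and no other section contradicts. It does not depend on the simulated figures. Those assume 214 evaluable subjects per arm, and the power comparison also assumes lognormal changes and a shift of 0.25. The primary analysis, the key secondary analyses and type I error control are unaffected.

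**What to change.** Delete the Sign Test sentence from Section 13.1.5 and keep the Wilcoxon rank-sum test with the Hodges-Lehmann estimate and its 95% confidence interval. The cost is one deleted sentence, and no useful analysis is lost.

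If the sponsor wants cover for arms that differ in shape, name in advance a two-sample method for the difference in medians, such as a bootstrap confidence interval, as a supplement to the rank-sum result and not a replacement. This costs one further sentence.

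A stratified (van Elteren) form of the rank-sum test would match the stratification used in neighbouring analyses. It is an optional extra and not part of this correction.

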13.1.5.1. Association of Biochemistry with Clinical Outcomes and Clinical Benefit

The association between biochemistry including ALP and bilirubin with clinical outcomes will be assessed and the clinical benefit of OCA using biochemistry as a surrogate endpoint will be evaluated. Detailed analysis will be described in the SAP.

Based on the association between biochemical changes and clinical outcomes described above, clinical benefit of OCA using biochemistry as a surrogate endpoint for key subpopulations of interest will be evaluated. This analysis will be further described in the SAP.

13.1.6. Exploratory Efficacy Analyses

13.1.6.1. Responder Analyses

The percentage of subjects with a decrease in ALP of $\geq 15\%$ and $\geq 40\%$ from Baseline will be summarized by treatment group. In addition, the percentage of subjects with ALP \leq ULN will be summarized by treatment group.

The percentage of subjects that meet the criteria of a responder based on each of the definitions below will be summarized by treatment group. The response classification at baseline will also be included in the summary:

- ALP $\leq 3x$ ULN and AST $\leq 2x$ ULN and total bilirubin \leq ULN ([Corpechot 2008](#))
- ALP $\leq 1.5x$ ULN and AST $\leq 1.5x$ ULN and total bilirubin \leq ULN ([Corpechot 2011](#))
- ALP $\leq 1.67x$ ULN and total bilirubin \leq ULN ([Momah 2012](#))
- Normal bilirubin (values \leq ULN) and normal albumin (values \geq lower limit of normal) ([Kuiper 2009](#))
- ALP $\leq 1.76x$ ULN ([Kumagi 2010](#))

Responder analyses will compare treatment groups using a Cochran–Mantel–Haenszel test stratified by the randomization stratification factor. Missing values will be considered as a non-responder.

13.1.7. Pharmacoeconomic and Health Outcomes Endpoints

Sufficient data will be collected on resource utilization and quality of life to undertake cost-effectiveness analyses that are relevant to the major countries taking part in this study. Resource utilization data on hospitalizations, healthcare provider visits, and medications will be combined with appropriate national unit costs to calculate a cost per patient per year in the study.

Quality of life data from patient-reported outcomes measures will be combined with survival data to calculate quality adjusted time in the study per patient. Cost-effectiveness analyses will report the incremental cost per major clinical outcome averted, liver-related death averted, life-year gained and quality-adjusted life year gained, including OCA as part of usual care versus usual care without OCA. Analyses will be conducted within the study and using a lifetime perspective. A separate economic analysis plan will be prepared and reported separately from this protocol.

13.1.8. Supportive Analysis

Per the International Conference on Harmonisation (ICH) E10 guidance, “where no obvious single optimal external control exists, it may be advisable to study multiple external controls”. In order to address the risks associated with the inclusion of a long-term placebo arm, supportive analyses of the primary endpoint will compare clinical outcomes in the OCA treatment arm to historical controls, which serves as an external control for supportive analysis.

In an attempt to avoid the inherent biases with historical controls and to maintain the integrity of this comparison, one can invoke matching methods to optimize comparability and find a historical control that is “similar” to a participating subject. The historical database control should be as similar as possible to the study population and should have been exposed to a similar standard of care (see [Section 5.5.2.3](#)).

A propensity score can be used to reduce bias through matching, stratification, regression adjustment, or some combination. Propensity scores use information from a pool of patients who do not participate in the study (historical controls) to identify what would have happened to participating subjects in the absence of the treatment. By comparing how outcomes differ for treated subjects relative to historical controls, it is possible to estimate the effects of the treatment between the treated subjects and the matched natural history subjects.

A full range of covariates across which the treatment and historical controls might differ will be considered to mitigate potential bias. Although the results of using matching controls are conditional only on the observed covariates, if one has the ability to measure many of the covariates that are believed to be related to the treatment assignment, then one can be fairly confident that approximately unbiased estimates for the treatment effect can be obtained. Both UK-PBC Group and the Global PBC Study Group formally collect numerous covariates that could be used for propensity score estimation including standard of care, eg, UDCA.

Historical controls will be chosen based on the same inclusion/exclusion criteria where possible. Propensity scores will be estimated using the available covariates that predict receiving the treatment. Only covariates and not outcome variables will be included in the propensity score estimation, to avoid biased results that are in favor of one treatment.

The covariates and factors collected in the historical databases will be specified in the SAP.

Propensity scores will be estimated first through a logistic regression model with treatment group as the dependent variable and the above covariates/factors as independent variables. Then the stratum boundaries are determined based on the propensity score values for both groups (OCA population and control [historical and randomized placebo]) combined or in the OCA population or historical control group alone. Based on recommendations in the literature, quintiles of the estimated propensity score from the combined group will be used to determine the stratum boundary cut-offs for the different strata.

The baseline characteristics between treated and natural history subjects in the matched dataset will be summarized and presented in a tabular format. Statistical methods such as Wilcoxon Rank-Sum test will be used to assess the balance for baseline covariates. The standardized difference and variance ratios for these covariates will also be calculated. In addition, box plots of propensity scores for treated and natural history subjects will be separately presented, to further assess the adequacy of matching.

A third-party statistician(s) will perform the propensity score modeling and matching. This third-party statistician(s) will be separate and independent from the statistician(s) who will assess the success of matching and perform efficacy analyses. Outcome events collected in the historical database are: death (liver-related and all-cause), liver transplant, HCC, and other. Other is defined as cirrhosis or decompensation such as ascites, variceal bleed, and encephalopathy.

The propensity score quintile will be then be used as the stratification factor in the stratified log rank test to compare randomized OCA-treated subjects in the ITT population and historical controls (Overall Historical Control Population: both the UK-PBC Group and Global PBC Study Group databases) on the following outcomes:

- Time to death (all-cause)
- Time to liver-related death
- Time to liver transplant
- Time to liver transplant or death (all-cause)
- Time to liver transplant or liver-related death

KM estimates of the distribution of the time-to-event will be tabulated and graphed by treatment group. The tabulation will include the KM estimate of the medians and corresponding 95% CIs if the medians can be estimated. The number and percent of subjects censored and with events will be presented. The hazard ratio and 95% CI will be determined based on a Cox regression model stratified by randomization strata to estimate the magnitude of the effect.

Sensitivity analyses will be conducted limiting to the separate individual historical control databases, ie, UK-PBC Group and Global PBC Study Group. To evaluate the robustness of the propensity score estimations, additional algorithms and factors may be considered.

Although the study is designed as a placebo-controlled study, the DMC may recommend changes to study conduct based on the pre-specified interim analyses (see [Section 13.1.12](#)), including the potential use of a revised primary efficacy analysis. This analysis would compare all subjects in the OCA population, to all control subjects (randomized placebo and historical controls) on time to liver transplant or death (all-cause), using similar statistical methodology as specified above.

Notably, the planned primary analysis would not be revised without prior agreement with regulatory authorities.

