13.1.1.1. Comparability of Historical Controls

Utilization of both historical control/observational databases (UK-PBC and Global PBC Study Group), with more than 6000 subjects each, allow for a rigorous subject level meta-analysis. The historical databases include long-term follow up, detailed subject-level information such as baseline clinical characteristics, longitudinal liver biochemistry, and long-term outcomes, and span a broad range of subject characteristics that may influence disease (disease state, age, gender, and regional differences in standard of care). Historical controls from both databases will be chosen based on the same study inclusion/exclusion criteria. Propensity score matching method will be utilized to select historical controls that match the treated subjects using available covariates. The adequacy of matching will be assessed by statistical methods described under [Section 13.1.8](#).

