13.1.3. Primary Efficacy Analysis

The primary efficacy endpoint will be the time to first occurrence of one of the following post-randomization:

- Death (all-cause)
- Liver transplant
- MELD score ≥ 15
- Hospitalization (as defined by a stay of 24 hours or greater) for new onset or recurrence of:
 - Variceal bleed
 - Hepatic encephalopathy (as defined by a West Haven score of ≥ 2)
 - Spontaneous bacterial peritonitis (confirmed by diagnostic paracentesis)
- Uncontrolled ascites (diuretic resistant ascites requiring therapeutic paracentesis at a frequency of at least twice in a month).

The primary efficacy analysis will compare OCA to placebo with respect to the primary efficacy endpoint using the ITT population. Only adjudicated events will be included in analyses. The 2 treatment groups will be compared using the log rank test stratified by the randomization stratification factor. Kaplan-Meier (KM) estimates of the distribution of the time-to-event will be tabulated and graphed by treatment group. The tabulation will include the KM estimate of the medians and corresponding 95% confidence intervals (CIs), if the medians can be estimated. The number and percent of subjects censored and with events will be presented. The hazard ratio and 95% CI will be determined based on a Cox regression model stratified by randomization strata to estimate the magnitude of the effect. The same analyses for primary efficacy endpoints will be performed for PP population as a sensitivity analysis.

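### In Section 13.1.8 the hazard ratio against historical controls is stratified by randomisation strata, while its paired log-rank test is stratified by propensity-score quintile

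*Protocol*

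**What the plan says.** Section 13.1.8 sets out the supportive comparison of randomised OCA subjects with historical controls.

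- **Test:** "The propensity score quintile will be then be used as the stratification factor in the stratified log rank test".
- **Estimate:** the hazard ratio and 95% CI are to be "determined based on a Cox regression model stratified by randomization strata to estimate the magnitude of the effect".
- **Source of that wording:** Section 13.1.3, the randomised primary analysis, also takes its hazard ratio from a Cox model "stratified by randomization strata to estimate the magnitude of the effect".
- **Meaning of the strata:** Section 9.4 allocates subjects "stratified by UDCA treatment (yes/no) and mean baseline bilirubin categories", so there are four cells, each given to a subject at randomisation.
- **Selection of controls:** Section 13.1.1.1 says "Propensity score matching method will be utilized to select historical controls that match the treated subjects using available covariates". Section 13.1.8 then checks balance in the matched data set by rank-sum tests, standardised differences, variance ratios and box plots.
- **Covariates:** the two databases "formally collect numerous covariates that could be used for propensity score estimation including standard of care, eg, UDCA"; the list is left to the SAP.
- **Quintile boundaries:** Section 13.1.8 names three possible bases and settles on the combined group, described there as "OCA population and control [historical and randomized placebo]) combined".

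No sentence puts the propensity score or its quintile into the Cox model.

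**The concern.** Stratifying by randomisation strata suits Section 13.1.3, where every subject was randomised. In Section 13.1.8 one of the two groups was not. The rule cannot be applied to that group as written, and the nearest workable substitute adjusts for two dichotomised factors, whereas the test adjusts for the whole propensity score.

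A stratified log-rank test is the score test of the Cox model that has the same strata. With different strata, the p-value and the confidence interval are no longer a pair and can disagree. The hazard ratio would also carry whatever imbalance remains after matching in covariates other than UDCA use and bilirubin category, although the protocol evidently wants further propensity adjustment at the testing step.

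Section 5.5.2.3 offers this comparison as a way to address bias in the placebo arm, for example from commercial OCA. Section 13.1.8 would also carry similar methods into a possible revised primary analysis on transplant or death.

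**Working it through.** **The plan's own figures.** The protocol gives no event count, power or expected hazard ratio for this comparison. Its figures belong to the randomised comparison and reproduce. With 60% placebo survival at 8 years, the hazard is λ = −ln(0.6)/8 = 0.0639 per year, and 0.6λ on OCA. With 4 years of accrual and 10 years in total, P(event) = 1 − [exp(−6λ) − exp(−10λ)]/(4λ), which is 0.398 on placebo and 0.263 on OCA, mean 0.331. Then 127/0.3308 = 384, and 384/0.9 = 427, against 428 stated. Nothing in this point changes them.

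**The rule read literally.** The score of a stratified Cox model is U = Σ over strata, Σ over events, of (x − x̄), where x is the treatment indicator and x̄ its risk-set mean. Controls without a stratum value are either dropped or placed in strata with no OCA subject. In a single-arm stratum x = x̄ at every event, so it adds nothing to U or to the information. No hazard ratio can be estimated.

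**The rule read generously.** The databases hold UDCA use and "longitudinal liver biochemistry, and long-term outcomes", so the four cells could probably be derived for controls, although the protocol does not say so. The model then adjusts for those two factors only.

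**Size without matching.** These are illustrations; their inputs are assumptions, not protocol figures. Take 214 OCA subjects, 856 controls, and one prognostic covariate outside the strata with HR 1.5 per SD, on which controls are sicker by δ SD.

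| δ (SD) | True HR | Cox by UDCA × bilirubin | Cox by propensity quintile |
|---|---|---|---|
| 0 | 1.0 | 1.00 | 1.00 |
| 0.25 | 1.0 | 0.91 | 0.99 |
| 0.5 | 1.0 | 0.82 | 0.97 |
| 0.75 | 1.0 | 0.75 | 0.97 |

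The third column is close to 1.5^(−δ), which is 0.90, 0.82 and 0.74 for the three shifts. With a true HR of 0.60, the two models give 0.61 and 0.61 at δ = 0, but 0.49 and 0.59 at δ = 0.5.

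A larger null set-up has 4,000 OCA subjects, 12,000 controls and four covariates at HR 1.4 per SD, each shifted by 0.1/0.2/0.3 SD. It gives 0.92/0.81/0.73 with randomisation-type strata and 1.00/1.00/0.98 with quintiles.

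**Size with matching.** A similar null set-up, assuming 90% on UDCA, 40% with bilirubin above ULN, and 1:1 nearest-neighbour matching with a 0.2 SD caliper, gives:

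| Analysis | 0.1 SD | 0.2 SD | 0.3 SD |
|---|---|---|---|
| Unmatched, Cox by UDCA × bilirubin | 0.89 | 0.78 | 0.70 |
| Matched, Cox by UDCA × bilirubin | 1.00 | 0.99 | 0.98 |
| Matched, Cox by propensity quintile | 0.99 | 0.98 | 0.98 |

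After good matching the choice of stratifier moves the hazard ratio by about 0.01 at most.

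**The case against.** The strongest objection is that the protocol matches first. Controls are selected on the propensity score, limited in Section 13.1.1 to those shown to be comparable, and checked for balance. The score therefore already acts on the hazard ratio through the choice of sample. This stands, and it limits the size of the problem. A reader might infer that the reported hazard ratio is simply unadjusted, or that the 0.92/0.81/0.73 above is what this plan would produce. The documents do not support either reading: those figures come from an unmatched analysis that the protocol does not specify, with every covariate assumed worse in controls.

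Matching does not rescue the wording, however. It gives unrandomised subjects no randomisation stratum, and the plan still stratifies the test by quintile while omitting this for the estimate. The matching ratio and caliper are not stated in the protocol, and poorer matching would leave more bias.

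A reader might also infer that naming randomised placebo in the boundary rule contradicts Section 5.5.2.3, which keeps historical and placebo comparisons separate. It does not. Placebo appears there only in setting stratum boundaries; the test itself compares OCA with historical controls. The bracketed wording fits the contingent pooled analysis described later in the section. This merits a clarification, nothing more.

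Finally, the analysis is supportive and outside the testing hierarchy of Section 13.1.10, and the revised primary analysis would need prior regulatory agreement. Both are true and keep the weight of the point modest.

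**Conclusion.** The mismatch is explicit, and the protocol itself fixes it; it is not a detail left to the SAP. The Cox stratifier in Section 13.1.8 cannot be applied literally to historical controls. Under the most generous reading it adjusts within the model for two factors only, and its interval does not correspond to the quintile-stratified test.

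The numerical consequence is uncertain and may be small. It is close to nil if matching balances the covariates, and grows towards the unmatched illustrations if matching is poor and controls differ in prognosis. A bias in favour of OCA follows only from the assumption that controls are sicker. The randomised primary hazard ratio, the 127 events and the 428 subjects are unaffected. The correction should still be made, because the same methods could pass into a revised primary analysis.

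**What to change.** In Section 13.1.8, change the Cox sentence so that the hazard ratio and 95% CI come from a model stratified by propensity-score quintile, as in the log-rank test.

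As a clarification only, state that for this comparison the quintile boundaries are set on OCA plus historical controls, and that randomised placebo subjects enter them only in the contingent pooled analysis.

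The cost is a one-line correction and one clarifying sentence in the protocol, carried into the SAP. No sample size, visit or data collection changes.
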